10.6 NON-INFECTIOUS LEUKOCYTOSIS

Initiation of treatment with the differentiating agents may lead to rapid WBC expansion not associated with infectious process and not manifesting with the signs and symptoms of IDH-Inhibitor Differentiation Syndrome (IDH-DS) discussed above.

In subjects with elevated WBC, prompt initiation of hydroxyurea is suggested, as per standard local practices (e.g., dose of 2 to 3 g PO twice or three times daily for WBC > 30×109 /L). In case of severe leukocytosis (WBC >100 x 109/L), use of leukapheresis may be appropriate. Subject should be regularly monitored for changes in WBC count and for new signs and symptoms of infection or IDH-Inhibitor Differentiation Syndrome (IDH-DS).

10.7 DISCONTINUATION OF RUXOLITINIB AND ENASIDENIB

Upon planned discontinuation of ruxolitinib it is recommended to taper off the drug over the course of 4-7 days and permissible to use prednisone daily during this period to blunt rebound of symptoms. Since patients will be on varying dosing regimens of ruxolitinib, investigators are urged to discuss the ruxolitinib taper plan with Study Chairs.

If a patient has to have ruxolitinib held abruptly for the occurrence of adverse events (e.g. major bleeding, significant thrombocytopenia, etc.), then the ruxolitinib may be stopped WITHOUT a taper and a pulse of prednisone may be utilized if deemed necessary by the Investigator.

Enasidenib may be interrupted or stopped without tapering.

10.8 EVALUATION DURING TREATMENT/INTERVENTION

Baseline evaluations are to be conducted within 28 days of the first study drug administration, unless otherwise indicated within the Schedule of Assessments outlined in **Table 4**. All scheduled visits will have a ± 7 days window unless otherwise stated or indicated within the Schedule of Assessments.

11. WHEN AND HOW TO WITHDRAW SUBJECTS

MPN-RC

A Phase II Open-label Study of Combined Ruxolitinib and Enasidenib Sinai

in Patients with Accelerated/Blast-phase Myeloproliferative Neoplasm or Chronicphase Myelofibrosis with an IDH2 Mutation

(Myeloproliferative Neoplasms Research Consortium [MPN-RC] 119)

In accordance with the Declaration of Helsinki and the guidelines of the country of the participating MPN-RC Clinical Study Center, each subject is free to withdraw from the study at any time. An Investigator also has the right to withdraw a subject from the study in the event of the patient suffering an intercurrent illness, adverse events, or other reasons concerning the health or well-being of the patient, or in the case of lack of cooperation by the patient. All serious adverse reactions need to be followed up until resolution and information returned to study coordinators.

Should a subject decide to withdraw after administration of study drug, or should the Investigator decide to withdraw the subject, all efforts should be made to complete and report the observations up to the time of withdrawal as thoroughly as possible. A final evaluation, the reason for, and the date of withdrawal must be recorded on the CRF. The last visit for each subject will be defined as a study discontinuation/ end-of-study visit, which will occur 30 (\pm 7 days) days after time of treatment withdrawal.

Subjects with clinically significant abnormal laboratory values as determined by the Investigator or who have ongoing clinically significant treatment-related adverse events during their last scheduled clinical evaluation will be monitored and treated until resolution or stabilization is achieved; or, in the event that the subject's condition is not likely to improve because of disease progression, until the cause of the abnormal test result or adverse event can be determined.

11.1 DATA COLLECTION AND FOLLOW-UP FOR WITHDRAWN SUBJECTS

The reason for and date of withdrawal from study drug treatment; and the reason for and date of withdrawal from the study will be recorded on the case report form (CRF). If a subject withdraws consent, every attempt will be made to determine the reason. If the reason for withdrawal is an adverse event or a clinically significant abnormal laboratory test result, monitoring will continue until the event has resolved or stabilized, until the subject is referred to the care of a local health care professional, or until a determination of a cause unrelated to the study drug or study procedure is made. The specific event or test result(s) must be recorded on the CRF. All evaluations will be performed, according to the protocol, 30 days (\pm 7 days) after the patient is withdrawn from treatment.

Patients will continue to be followed for long term survival every 3 months by telephone encounter or medical record review to determine the following variables: alive versus deceased and type of current therapy. Patients will be followed for this long term survival data until death, confirmed lost to follow up, or a maximum of 1 year after end of treatment.

A subject will be considered to be lost to follow-up if all of the following criteria have been met:

- 1. More than three phone calls to the subject are unanswered.
- 2. A next of kin is contacted and no information is available.
- 3. The referring physician is contacted and no information is available.
- 4. A telegram or certified letter is unanswered.

11.2 DURATION OF FOLLOW-UP

The patient will have an end of study visit at 30 days after discontinuation of the protocol treatment, with a window of ± 7 days, to assess for AEs.

Patients will continue to be followed for long term survival every 3 months by telephone encounter or medical record review to determine the following variables: alive versus deceased and type of current therapy. Patients will be followed for this long term survival data until death, confirmed lost to follow up, or a maximum of 1 year after end of treatment.

in Patients with Accelerated/Blast-phase Myeloproliferative Neoplasm or Chronicphase Myelofibrosis with an IDH2 Mutation

(Myeloproliferative Neoplasms Research Consortium [MPN-RC] 119)

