3. STUDY SCHEMA

Eligible patients with signed consent who have completed all requisite screening tests and procedures are to start Cycle 1 Day 1 within 30 days of signing consent.

All adverse events captured during the first 28 days of treatment with Ruxolitinib and Enasidenib will be used to assess safety and tolerability in the first 6 patients on study.

Cycles will be a minimum of 28 days.

Following cycle 6, response will be assessed by IWG/ELN consensus criteria and patients will continue treatment if response was deemed a CR/CRi/PR or CBR for MPN-AP and MPN-BP patients. For chronic phase MF, response will include CR/PR and clinical improvement.

Patients will continue to be followed post treatment for long term survival every 3 months for up to 12 months by telephone encounter or medical record review to determine the following variables: alive versus deceased and type of current therapy.

*Ruxolitinib dosing based on platelet counts; Enasidenib 100 mg for MPN-AP or MPN-BP and 50 mg for chronic phase MF for cycle 1

in Patients with Accelerated/Blast-phase Myeloproliferative Neoplasm or Chronicphase Myelofibrosis with an IDH2 Mutation

(Myeloproliferative Neoplasms Research Consortium [MPN-RC] 119)

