Study Product(s), Dose, Route, Regimen	Ruxolitinib and enasidenib will be given orally in 28-day cycles. Ruxolitinib dose will be given per protocol, enasidenib will be given at 100 mg daily on enrollment for patients with accelerated and blast phase myelofibrosis regardless of platelet count. Patients with chronic phase myelofibrosis will receive enasidenib at starting dose of 50mg daily for cycle 1. The dose of enasidenib will be increased to 100mg for cycle 2 if the platelet count stays above 50,000 at the end of cycle 1 (Table 3a) and no other therapy emergent SAE of grade ≥ 2 developed (except grade 2 hyperbilirubinemia that is acceptable for dose escalation)

The Tisch Cancer Institute

A Phase II Open-label Study of Combined Ruxolitinib and Enasidenib

in Patients with Accelerated/Blast-phase Myeloproliferative Neoplasm or Chronicphase Myelofibrosis with an IDH2 Mutation

(Myeloproliferative Neoplasms Research Consortium [MPN-RC] 119)

Duration of administration	Duration of treatment anticipated to be at least 6 months. Responders will continue therapy indefinitely unless progression of disease occurs, toxicity warranting discontinuation of therapy is observed, or at the discretion of the treating physician.
	The primary endpoint of this study is best overall response, defined as partial response or better (CR+PR+Cri), and will be defined as the best response by Cycle 6 of combination therapy. All patients meeting the eligibility criteria who have signed a consent form and have begun treatment will be evaluable for response. Any evaluable patient not meeting the definition for response will be deemed as having a non- response.
Statistical Methodology	The largest overall response rate where the proposed combination treatment regimen would be considered ineffective in this patient population is 5%, and the smallest response rate that would warrant subsequent studies with the proposed regimen is 25%. This is based on retrospective analysis applying the 2013 IWG Response Criteria to patients treated with ruxolitinib. A Simon's two-stage minimax design will be employed to test the null hypothesis that the true overall response rate in this patient population is at most 5%.

MPN-RC

MPN-RC A Phase II Open-label Study of Combined Ruxolitinib and Enasidenib Sinai in Patients with Accelerated/Blast-phase Myeloproliferative Neoplasm or Chronic-

phase Myelofibrosis with an IDH2 Mutation (Myeloproliferative Neoplasms Research Consortium [MPN-RC] 119)

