22.2 SECONDARY ENDPOINTS

To additionally assess the efficacy of the combination of ruxolitinib with enasidenib in patients with accelerated or blast-phase disease after 6 cycles of combined therapy using complete (CBR) or partial blast response (PBR). CBR and PBR will be defined according to Appendix A. This will be calculated similarly to the primary endpoint for the MPN-AP/BP cohort.

To assess the efficacy of the combination of ruxolitinib with enasidenib in patients with PMF, post-PV MF, or post-ET MF in chronic phase and 4-9% blasts as assessed by the modified 2013 International Working Group (IWG) Response Criteria, after 6 months of combined therapy. This will be calculated similarly to the primary endpoint for the MPN-AP/BP cohort.

Adverse events: All eligible patients that have been initiated treatment will be included in the calculation of adverse event rate(s). The maximum grade for each type of adverse event will be tabulated for each patient, and frequency tables will be reviewed to determine patterns. Additionally, the relationship of the adverse event(s) to the study treatment will be taken into consideration. Adverse events will be summarized overall and by cohort.

Overall Survival (OS) will be defined as the time from first treatment with the ruxolitinib/enasidenib combination to death by any cause. Patients will be considered censored at the last known date alive, if death is not documented. OS will be estimated using the Kaplan-Meier method.

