27. WITHDRAWAL OF SUBJECTS

Treatment with study drugs is to be discontinued when any of the following occurs:

- Lack of any response by 6 cycles of combined enasidenib and ruxolitinib therapy (any effort should be made to provide therapy to the patient in a safe way for at least 3-6 cycles for proper assessment of potential efficacy).
- Adverse event(s) that, in the judgment of the Investigator, may cause severe or permanent harm or which rule out continuation of study drug
- Withdrawal of consent
- Lost to follow up
- Toxicity requiring dose modification/treatment suspension, without recovery to baseline, in a patient with less than a CRi
- Death

MPN-RC

The patient will have an end of study visit at 30 days after discontinuation of the protocol treatment ± 7 days to assess for AEs.

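### Survival follow-up is capped at 1 year after each patient's own end of treatment, so Kaplan-Meier OS is subject to outcome-dependent censoring, mainly beyond about month 18

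*Combined protocol and SAP*

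**What the plan says.** Section 22.2 defines OS as the "time from first treatment with the ruxolitinib/enasidenib combination to death by any cause". On censoring it says: "Patients will be considered censored at the last known date alive, if death is not documented". On the estimator: "OS will be estimated using the Kaplan-Meier method".

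Section 11.2 follows patients for survival until they die, are confirmed lost, or reach "a maximum of 1 year after end of treatment". Section 11.1 and Table 4 footnote 15 repeat this rule, and the study schema (Section 3) has post-treatment contact "every 3 months for up to 12 months by telephone encounter or medical record review".

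Treatment duration is open-ended and depends on outcome. Section 27 lists among the reasons to stop: "Lack of any response by 6 cycles of combined enasidenib and ruxolitinib therapy". It also lists harmful adverse events and some unresolved toxicity. The study summary (Section 4) says: "Responders will continue therapy indefinitely unless progression of disease occurs". Sections 10 and 12.0 agree.

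No section sets a common OS cut-off date, a fixed follow-up time from first dose, a limit on how far the curve is reported, or a sensitivity analysis for dependent censoring.

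**The concern.** The OS clock starts at first dose, but the end of observation is counted from the last dose. Each patient can therefore be observed for at most the treatment duration plus 12 months. Since response, progression and toxicity decide treatment duration, they also decide when a living patient is censored.

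Kaplan-Meier treats a censored patient as having the same future hazard as those still at risk. Under this rule, survivors who stopped early leave first and the late risk set fills with patients who stayed on treatment. If the two groups differ in prognosis, the late part of the curve is biased.

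OS in advanced-phase patients is a stated secondary objective (Section 7.2). In a single-arm trial, readers will set the curve beside historical survival such as that in Section 6.1.

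**Working it through.** **Plan's own figure.** There is none for OS: no event count, power or precision is given. Table 6 concerns response only. It recomputes as stated (power 0.903 at a 25% response rate, stated as 0.90) and does not bear on this point.

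**Step 1: when the cap falls.** A cycle is 28 days (Section 10). Cap month = cycles × 28 / 30.4375 + 12.

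| Cycles completed | Cap (months from first dose) |
|---|---|
| 1 | 12.9 |
| 3 | 14.8 |
| 6 | 17.5 |
| 12 | 23.0 |
| 24 | 34.1 |

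The cap cannot censor anyone before month 12, so it causes no bias up to that point. Survivors who complete 1 to 6 cycles are all censored between about months 13 and 17.5.

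**Step 2: a hand calculation.** Assumptions, not in the documents: exponential survival, all non-responders stop at cycle 6, and 25% respond (the design alternative in Section 20.1). Take medians of 9 months (non-responders) and 36 months (responders).

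- True survival at month 24: 0.75 × 2^(−24/9) + 0.25 × 2^(−24/36) = 0.276.
- Survival at month 17.52, when the non-responders are censored: 0.75 × 2^(−17.52/9) + 0.25 × 2^(−17.52/36) = 0.373.
- From then on only responders are at risk, so the Kaplan-Meier limit at month 24 is 0.373 × 2^(−6.48/36) = 0.373 × 0.883 = 0.329.
- Bias: 0.329 − 0.276 = +0.053, about 5 points.

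With medians of 6 and 18 months the same steps give 0.226 × 2^(−6.48/18) = 0.176 against 0.146, about +3 points.

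**Step 3: simulation over a range.** The first set has 16 scenarios of 600,000 patients each. Assumptions: response rate 25% or 45%; non-responder median 4, 6, 9 or 12 months; responder median 18 or 36 months; half of non-responders stop between cycles 1 and 6 and the rest at cycle 6; responders stay on treatment a further mean of 12 months. The second set also lets non-responders stop uniformly over cycles 1 to 6. Entries are Kaplan-Meier minus true OS, in percentage points.

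| Month | 16 scenarios | Second set |
|---|---|---|
| 12 | 0 | 0 |
| 15 | +0.1 to +0.2 | +0.1 to +0.4 |
| 18 | +0.5 to +1.3 | +0.9 to +2.5 |
| 24 | +1.6 to +6.1 | +3.3 to +7.2 |

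A bias of about +2 points at month 18 appears only when non-responders stop uniformly over cycles 1 to 6.

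**Step 4: does the direction hold?** All rows use 25% response.

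- Equal hazard in both groups (median 9 months): bias zero throughout.
- Medians 6 and 18 months, with 15% of non-responders given a 60-month median: +1.5 at month 24.
- The same with 30% of non-responders: −0.5 at month 24 and −3.5 at month 36.

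**Step 5: precision.** With 22 patients the sampling SD of 24-month OS is about 10 to 12 points. Of 20 patients, about 2 to 5 remain at risk at month 18 and 1 to 3 at month 24.

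**Step 6: common cut-off.** When everyone is followed to one calendar date, the simulated bias disappears, because administrative censoring then depends only on entry date.

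**The case against.** The best defence is that this hardly matters here. OS is descriptive, and Section 22.2 plans no landmark estimate, comparison or test. Section 6.1 puts median survival below 12 months with more than 10% blasts, and at 6 to 7 months for treated blast-phase patients, so the median probably falls before the cap can act. Where the bias becomes visible, few patients are left and sampling error exceeds it. All of this stands and keeps the point small. It does not remove it: a confidence interval describes sampling error and does not correct a systematic shift.

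The second defence concerns direction. Patients censored by the cap have already survived a year off treatment, and those doing worst have mostly died by then. Section 6.1 calls allogeneic transplant the only potentially curative option, so a patient might stop early and do well. This also stands: the upward sign is probable, not established.

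Two stronger readings are therefore unsupported. A reader might infer that the curve is inflated from month 13. Month 13 is only the earliest possible cap, and the computed bias stays under 0.5 points at month 15. A reader might also infer that the plan's late survival figures must flatter the regimen. The plan names no such figures, and the sign rests on a hazard difference that the documents do not give.

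**Conclusion.** The concern holds in limited form. Followed exactly, the plan ties OS censoring to treatment outcome, and the plain Kaplan-Meier estimate makes no allowance for it. If early stoppers keep a worse hazard, the curve is probably biased upward, mainly beyond about month 18: about +0.5 to +2.5 points at month 18 and about +2 to +7 at month 24.

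These sizes rest on assumed exponential survival, medians and stopping patterns. If long survival after early stopping is common, the bias shrinks, vanishes or reverses. OS to month 12 is unaffected by the cap, median OS probably is too, and the Simon decision uses response only. This is a cheap improvement to a secondary endpoint and no threat to the trial's main conclusion.

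**What to change.** In Sections 11.1 and 11.2, Table 4 footnote 15 and the schema, replace the cap with vital-status follow-up of all patients, on or off treatment, to one common calendar cut-off. Use the existing 3-monthly call or record review. In Section 22.2, censor surviving patients at that date, or at the last known date alive if lost earlier.

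Set the cut-off late enough that nobody is followed for less time than early stoppers are now. They can reach month 17.5, so 18 to 24 months after the last patient's first dose would do. With the 15-month accrual in Section 21, that is 15 + 18 = 33 to 15 + 24 = 39 months after trial start. A cut-off 12 months after the last first dose would be too early: it shortens follow-up for late enrollees and leaves only about 1 patient at risk at month 24.

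If the cap is kept, report Kaplan-Meier OS only to about 12 months from first dose, or label later estimates as subject to outcome-dependent censoring.

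The cost of the first option is a few more calls or record checks and a later final OS date. The second costs a shorter or qualified curve. Neither changes treatment.

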11.3 REMOVAL OF PATIENTS FROM PROTOCOL THERAPY

Patients will be removed from therapy when any of the criteria listed in When and How to Withdraw Subjects section apply. Notify the Principal Investigator and document the reason for study removal and the date the patient was removed in the Case Report Form.

11.4 PATIENT ACCRUAL

MPN-RC

Subjects are considered evaluable as long as they have signed informed consent, are eligible for participation and started study treatment. The maximum sample size in the Phase II (accelerated/blast-phase) is 20 evaluable patients. Allowing for enrollment of up to 2 additional patients to account for ineligibility, cancellation, major treatment violation, or other reasons, this study will enroll a maximum of 22 patients in the Phase II AP/BP cohort. The maximum sample size in the chronic phase MPN is 9 evaluable patients. Allowing for enrollment of up to 1 additional patient, this study will enroll a maximum of 10 patients in the descriptive chronic phase MPN cohort. Therefore, a maximum total of 32 (22 + 10) patients will be enrolled in the trial.

12.0 STUDY TIMELINES

Baseline evaluations are to be conducted within 30 days of the first study drug administration, unless otherwise indicated within the Schedule of Assessments outlined in **Table 4**. All scheduled visits will have a ± 7 days window unless otherwise stated or indicated within the Schedule of Assessments outlined below.

Ruxolitinib and enasidenib will be given orally in 28- day cycles. Attempts will be made to provide an adequate treatment period with the combination of at least 6 cycles, unless significant toxicity is observed, to account for delayed time to response observed with biologic agents. Interval Milestone Response Assessment (IMRA) can be performed at the beginning of any cycle after cycle 1 if specific milestones are achieved that will prompt such an evaluation. Specific milestones that will prompt assessment consist of clearance of blasts from peripheral blood in accelerated/blast phase patients, which will prompt bone marrow aspirate and biopsy. In addition progression of disease (as determined by an increase in blasts in the peripheral blood - defined as doubling of blasts % and achieving more than 10% in the chronic phase patients at least 7 days apart) will prompt IMRA. Responders will continue therapy indefinitely unless progression of disease occurs, toxicity warranting discontinuation of therapy is observed, or at the discretion of the treating physician. Patients will have an end of study visit for a safety follow-up at 30 days after their last dose of therapy.

13.0 STUDY ENDPOINTS

13.1 PRIMARY ENDPOINT

• The proportion of treated accelerated-phase and blast-phase MPN patients (primary cohort) that achieve a best response of either complete response (CR), Partial Response (PR), or complete response with incomplete recovery of counts (CRi), when treated with the combination of ruxolitinib with enasidenib within 6 cycles of combined therapy.

13.2 SECONDARY ENDPOINTS

• To assess the efficacy of the combination of ruxolitinib with enasidenib in patients with accelerated-phase and blast-phase disease using complete (CBR) and partial blast response (PBR).

in Patients with Accelerated/Blast-phase Myeloproliferative Neoplasm or Chronicphase Myelofibrosis with an IDH2 Mutation

(Myeloproliferative Neoplasms Research Consortium [MPN-RC] 119)

- The proportion of treated patients with MF-CP and 4%-9% circulating blasts that achieve complete response (CR) Partial Response (PR), clinical improvement (CI) with the combination of ruxolitinib and enasidenib within 6 cycles of combined therapy.
- To assess the impact of the combination of ruxolitinib with enasidenib on the overall survival of advanced phase MPN patients

